PIMs are associated with the Geriatric Problems that are common in Older Dialysis Patients: Older patients make up 46% of adults on dialysis in the U.S. Compared to older adults without kidney failure, older dialysis patients have at least double the rates of geriatric problems including falls, cognitive impairment, hospitalizations, and polypharmacy. Potentially inappropriate medications (PIMs) are a major modifiable risk factor for these conditions, not yet explored in dialysis patients. PIMs convey greater risks than benefits for most older adults. This risk is attributable to age-related changes in pharmacokinetics and pharmacodynamics. Older dialysis patients also have uremic toxins that can alter hepatic drug metabolism (i.e., cytochrome p450 inhibition). Older dialysis patients commonly take PIMs to treat symptoms associated with end-stage renal disease (ESRD), such as anxiety, muscle cramps, or pain (e.g., benzodiazepines, muscle relaxants, opioids), or to lower blood pressure (e.g., α -blockers and central α agonists). Because older dialysis patients have increased vulnerability to PIMs, reducing PIM use may prevent geriatric problems and related hospitalizations.

A Deprescribing Intervention Designed for Dialysis Units may Improve Health Outcomes:

Deprescribing interventions have been effective at reducing both PIM use and hospitalizations in community dwelling older adults. Such interventions frequently involve multidisciplinary care teams and/or patient education tools. However, no reports describe deprescribing interventions in U.S. dialysis units. To identify an effective approach, the contextual factors of dialysis need to be considered. Dialysis units often place a high priority on efficient patient turnover, are highly regulated, and have a separate electronic health record. Also, there are unclear terms of shared responsibility for medication management among multiple prescribers (primary care, nephrology, other specialists). Given this unique context, there are critical needs both for key stakeholder input on deprescribing intervention elements and mode of delivery, and for an evaluation of a novel deprescribing program's acceptability and practicality.

Design & Procedures

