- We will not administer the chair stand test during COVID-19 restrictions.
- After the physical distancing orders are lifted, we will attempt to complete any incomplete study procedures in-person: memory testing with modified MOCA (or the TRAILS and SLUMS tests), as well as the chair stand test required for assessment of frailty in subjects age 55-64.

Aim 2 -

We used the qualitative data from Aim 1 to design a deprescribing quality improvement program (QIP) for dialysis patients. We are seeking IRB approval for evaluation of this deprescribing QIP.

Brief Description of Deprescribing QIP: The dialysis deprescribing team (pharmacist, nurse, physician) will conduct the process of deprescribing in patients aged 55 and older who have been undergoing dialysis for at least 3 months and have regular use of a PIM based on their Duke electronic medical record (EMR). PIMs for deprescribing will include antihypertensive PIMs (alpha blockers and central alpha agonists) and psychoactive medications, such as gabapentinoids, muscle relaxants, and Z-drugs (e.g., zolpidem). The team will also conduct chart review to discern if the patient is a candidate for deprescribing the specific PIM. After identification of eligible patients, the deprescribing team will provide a deprescribing recommendation (including instructions for deprescribing the PIM) to the nephrologist (or other dialysis provider). If a patient agrees to attempt deprescribing a PIM, the team will supervise implementation and monitoring of the deprescribing.

Deprescribing PIMs is considered a best practice for providing care to older adults with multiple comorbidities. It can improve quality of life, reduce medication related problems and lower financial burden to patients.¹ It is consistent with the American Geriatrics Society's guiding principles to make clinical decisions that optimize benefit and minimize harm.² Deprescribing, as part of routine geriatrics care, carries minimal risk. It is not routine for dialysis clinics; however, a Canadian dialysis deprescribing QIP demonstrated favorable preliminary outcomes on reducing polypharmacy.³

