Decision-making	The nephrologist decides whether to proceed with the recommendation and talk with the patient on their own. Research activity: Questions to nephrologist about acceptability of the recommendation (see text)	If approval from nephrologist, study team talks to patient about recommendation and that nephrologist supports the recommendation. education to patient about medication risk and process for deprescribing. Team asks if patient is willing to proceed with deprescribing
Deprescribing	If patient agrees, Nephrologist will provide instructions for deprescribing. Research activity: Questions to nephrologist about acceptability of the recommendation (see text) and deprescribing attempts Research activity: After a patient decides (either for or against deprescribing), they will be approached for consent for an interview and/or survey. This approach will be by recruitment letter mailed and/or provided in person at the dialysis clinic. We will document deprescribing in medical record and to pharmacy.	If patient agrees, the deprescribing team will provide instructions for deprescribing. Research activity: After a patient decides (either for or against deprescribing), they will be approached for consent for an interview. This approach will be by recruitment letter mailed and/or provided in person at the dialysis clinic. We will document deprescribing in medical record and to pharmacy.
Monitoring	Deprescribing team will assist patient with any issues during deprescribing step AND contact patient after a month to check on progress and ask about symptoms.	Deprescribing team will assist patient with any issues during deprescribing step AND contact patient after a month to check on progress and ask about symptoms.

Aim 2 Data collection: We are collecting data for program evaluation. we will assess demand, deprescribing attempts, change in PIM burden (number of PIMs) and feasibility (acceptability and practicality),

Demand: We will assess demand from chart review and define demand as the proportion of patients with a specific PIM divided by all patients with PIMs.

Deprescribing Attempts: We will assess number (and %) of deprescribing attempts in each format of the QIP. The denominator would be total number of patients who were approached for deprescribing decision-making. The approach for each format:

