- QIP – Provider Communication Only: We will ask dialysis providers if the patient agreed to deprescribe after a month.
- QIP – Provider / Patient Communication: We will collect information from the deprescribing team on whether the patient agreed to deprescribe.

participants who agreed to deprescribed were called after 3 months to see if they remained off PIM or at a lower dose of the PIM

Change in PIM burden: We will assess change in PIM burden as measured by Sustainability at 3 months; of those who can be reached, proportion of patients who remain off PIM at at a lower dose at 3 months. Participants who agree to deprescribe will be called after 3 months to see if they remain off PIM or at a lower dose of the PIM.

Time frame: 3 months.

Provider Acceptability: For the QIP-Provider Communication only format, we want to assess provider acceptability of the QIP recommendation. Specifically, When the nephrologist (or other dialysis provider) receives the recommendation from the deprescribing team, they will receive a short survey with two primary questions: 1) Will you implement this deprescribing plan? 2) If not, would you support implementation of this deprescribing plan if you had assistance from the deprescribing team? At the end of the month, we will ask the nephrologist some questions about the deprescribing plan: What worked about the deprescribing program recommendation? What did not work?

Patient acceptability: In both formats, we will assess patient acceptability. After a patient decides (either for or against deprescribing), they will receive a recruitment letter (either mailed to them, or given to them by a member of their care team) or may be called or approached in-person at the dialysis clinic to invite them to participate in an interview and a set of surveys. Patients will be able to choose to participate in data collection alone (baseline surveys and again at 3 months), or complete both an interview and the surveys. The consent process and interview will either be by phone or in person at the dialysis clinic. A description of the logistics for interviews is as described for Aim 1. The interviews will be audio recorded and later transcribed by an experienced transcriptionist. We expect to conduct interviews in 12-15 subjects. The focus of the interviews will be on acceptability of the clinical program (e.g., experience, perceived burden, negative consequences or side effects).

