Practicality: We can assess practicality in the QIP – across both Provider Only and Provider/Patient communication formats in the following measures:

- Time (in days) spent awaiting provider response to recommendation
- Time (in days) to initial patient communication
- Number of attempts to reach patient, number of conversations, and length of conversations

Additional data collected for Aim 2 is listed below. This data will be obtained from the medical record and through patient communication for the clinical program. We will also assess for clinical events by self-report and/or medical records.:

- Age / DOB (if age >89, will record as age 90)
- Gender
- Race
- Ethnicity
- PIM prescription
- Length of time on dialysis
- Comorbidities
- Medication counts
- Presence of adverse drug withdrawal event (ADWE), type of ADWE, and if associated with unscheduled clinic visit and/or serious adverse event.

Geriatric Assessment: Recent studies suggest that decisions around medications are related to other geriatric problems, such as mobility, cognitive dysfunction, and patient preferences. Therefore, we plan to ask patients to complete a geriatric assessment. The geriatric assessment will be administered via REDCap survey. Either study staff will assist patients with completion of the assessment remotely (via telephone call or zoom), or patients may complete the assessments on their own via an emailed REDCap link. Surveys include: geriatric assessment of mood, medication adherence, nutritional status, social support, what matters most, and mobility via the following survey instruments: Patient Health Questionnaire-9, Morisky Medication Adherence Survey, Health Outcomes Priorities, CDC Falls risk checklist, Modified Medical Outcomes Study Social Support Scale, Received Social Support & Satisfaction Measure, Simplified

Nutritional Appetite Questionnaire, Modified Gait Efficacy Scale, Functional Assessment, Patient and Caregiver Participant Survey, Cognitive Change Index, and Questions on Your Experience Completing the GOLD.

At a 3 month follow up, patients will be asked to repeat 4 of these surveys (Patient Health Questionnaire-9, CDC Falls Risk Checklist, Cognitive Change Index, and Functional Assessment), as well as an additional question: "Have you fallen in the last 3 months?" The 3-month surveys and additional question will be completed within 2 weeks of the exact 3 months date of baseline data collection.

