- Aim 1 Exclusion Criteria: Advanced dementia, those receiving hospice, and non-English speaking.

For Aim 1, our purposive sampling plan is to obtain a sample of older dialysis patients age ≥ 55 that includes at least two individuals in each of the following categories: 1) PIM (taking one vs. not), 2) dialysis vintage (≥ 6 months or < 6 months), and 3) level of independence in activities of daily living (independent or some dependence) this will often be indicated by whether they require assistance daily with medication administration. We will aim to include at least 50% under-represented minority patients.

Aim 2 Selection of Nephrologists and Nephrology staff participants:

For QIP Provider Communication Only, we will enroll Nephrologists and Advanced Practice Providers. Inclusion criteria for provider participation is that they must be employed by Duke and see patients at a

Duke affiliated DaVita hemodialysis (HD) clinic where Duke nephrologists serve as medical directors and rounding physicians.

Aim 2 Patient selection:

While this is a clinical program, the research evaluation part of Aim 2 will involve interviews and surveys with patients who participate in the program. Potential subjects will be identified by the research team utilizing Duke and DaVita dialysis medical records of dialysis patients, and confirming eligibility requirements with the nephrologist.

Consent will be required for patients to participate in this portion of Aim 2.

Aim 2 Inclusion Criteria: Patients must be aged ≥ 55 , have received dialysis for at least 3 months and have at least one active target PIM prescription. Subjects must be receiving dialysis at a Duke affiliated DaVita hemodialysis (HD) clinic where Duke nephrologists serve as medical directors and rounding physicians. Study participants must have a Duke primary care physician or prescriber of their PIM, and must use a pharmacy that utilizes electronic prescribing (i.e., Surescripts) so that we can examine medication usage by verifying 2 refills of a PIM (gabapentin, muscle relaxant, or anticholinergic) within prior 6 months.

Aim 2 Exclusion Criteria: Patients may not participate if they have been diagnosed with advanced dementia, are receiving hospice, do not speak English, or reside in a long-term care facility.

Subject Recruitment and Compensation

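### The 3-month measure of PIM burden follows only the deprescribed drug, so a patient switched to another PIM can count as a success with no fall in the number of PIMs

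*Combined protocol and SAP*

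**What the plan says.** In Design & Procedures, the opening of Aim 2 Data collection lists the outcome as "change in PIM burden (number of PIMs"). The paragraph headed Change in PIM burden then measures it by 3-month sustainability: "of those who can be reached, proportion of patients who remain off PIM at at a lower dose at 3 months". The status is found by telephone: "Participants who agree to deprescribe will be called after 3 months to see if they remain off PIM or at a lower dose of the" drug in question.

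Three places name PIM classes, and the lists differ:

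- Background & Significance gives as examples "e.g., benzodiazepines, muscle relaxants, opioids), or to lower blood pressure".
- The Brief Description of the Deprescribing QIP says "PIMs for deprescribing will include antihypertensive PIMs (alpha blockers and central alpha agonists) and psychoactive medications, such as gabapentinoids, muscle relaxants, and Z-drugs".
- The Aim 2 inclusion criteria refer to "verifying 2 refills of a PIM (gabapentin, muscle relaxant, or anticholinergic) within prior 6 months".

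The list of additional Aim 2 data, drawn from the medical record and patient communication, includes PIM prescription and "Medication counts". Neither has a stated time point or a link to the 3-month measure.

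**The concern.** The outcome is named as a count of PIMs, but it is scored on the status of one drug. The two can part company when the stopped drug is replaced. The Background makes replacement foreseeable. It describes PIMs as treatment for continuing complaints (anxiety, cramps, pain) or for blood pressure, and it says that responsibility for medication is shared unclearly among several prescribers.

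Benzodiazepines and opioids are called PIMs in the Background but are named in neither of the other two lists. It is therefore unclear whether a switch to one of them would be noticed, or counted as a PIM if it were.

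At stake is what the sustainability proportion can be taken to show. The overall objective concerns a strategy to reduce inappropriate prescribing. A figure that cannot separate stopping a PIM from exchanging it does not show whether PIM burden fell.

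**Working it through.** **Inputs**

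- Outcome as named: number of PIMs (Aim 2 Data collection).
- Outcome as measured: x/n, where n is the number who agreed and were reached at 3 months, and x is the number of those with the target PIM stopped or reduced (Change in PIM burden).
- n is not stated. Patient Recruitment for Aim 2 caps recruitment at 30 across both formats, and patients who decided against deprescribing are also invited. So 30 is the upper end if the measure is confined to recruited patients; 20 and 10 are assumed smaller values.
- x, and k (the patients in x who have a replacement PIM), are assumptions. The plan gives no expected sustainability rate, substitution rate, alpha or power, so there is no figure to reproduce.

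**Step 1: score the possible patients both ways**

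| Status at 3 months | Change in number of PIMs | Target-PIM measure |
|---|---|---|
| Target PIM stopped, no new PIM | −1 | Success |
| Target PIM stopped, another PIM started | 0 | Success |
| Target PIM back at its original dose | 0 | Not a success |

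The last two rows have the same number of PIMs and opposite scores.

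**Step 2: look for anything that closes the gap**

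- The one-month contact (deprescribing steps table; Data & Safety Monitoring) covers progress, symptoms, tolerance and adverse drug withdrawal events. It does not mention new drugs.
- The 3-month follow-up repeats four surveys and adds a falls question. None is described as a medication review.
- PIM prescription could show a switch if taken at baseline and at 3 months, but the plan does not say that it is.
- A total medication count would not show a one-for-one swap.

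**Step 3: size**

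Proportion not counting substituted patients = (x − k)/n. The difference from x/n is k/n.

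- Per substituted patient: 1/30 = 3.3 points; 1/20 = 5 points; 1/10 = 10 points.
- Relative excess, with s = k/x, is 1/(1 − s): 1.00 at s = 0, 1.11 at 10%, 1.25 at 20%, 1.43 at 30%.

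Illustrations, all counts assumed, with 95% Wilson intervals:

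| n | x/n | k | (x − k)/n | Difference |
|---|---|---|---|---|
| 30 | 24/30 = 80.0% (62.7 to 90.5) | 0 | 24/30 = 80.0% | 0 |
| 30 | 24/30 = 80.0% (62.7 to 90.5) | 5 | 19/30 = 63.3% (45.5 to 78.1) | 5/30 = 16.7 points |
| 20 | 16/20 = 80.0% (58.4 to 91.9) | 3 | 13/20 = 65.0% (43.3 to 81.9) | 3/20 = 15.0 points |

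The intervals are wide in any case, but they describe sampling error only. They make no allowance for substitution.

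**The case against.** The best reply is that the plan nowhere says that a switched patient counts as a success. The sustainability sentence speaks of being off PIM, with no article, under a heading about PIM burden. On that reading a patient moved to another PIM is not off PIM. This stands to the extent that the problem is inferred from silence and not from a stated rule. It does not remove the problem, because the other half of the criterion, a lower dose of the PIM, makes sense only for one particular drug, and the described call asks about nothing else.

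It also stands that Aim 2 is a descriptive feasibility evaluation whose hypothesis concerns acceptability and practicality, and that the PIM prescription item is already collected.

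A reader might infer more than the documents support:

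- *That sustained deprescribing is overstated.* No substitution rate is given. A swap leaves the result for the target drug correct; only the inference to PIM burden is affected.
- *That benzodiazepines and opioids fall outside the program's list.* That list is open-ended ("psychoactive medications, such as gabapentinoids, muscle relaxants, and Z-drugs (e.g., zolpidem") and excludes neither. They are unnamed, which is an ambiguity.
- *That replacement drugs would hide withdrawal events.* Data & Safety Monitoring counts worsened symptoms as such events. It seeks them at one month by record review and direct contact, and patients can reach the team earlier.
- *That patients would be moved to a riskier drug.* The Background lists the classes together without ranking them.
- *That this proportion will be carried into the later trial.* Data Analysis & Statistical Considerations names intraclass correlations and standard errors as informing sample size. It does not name this proportion.

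**Conclusion.** The point holds as a mismatch between the outcome as named and the outcome as measured. If substitution occurs, the 3-month proportion is too favourable as a measure of reduced PIM burden, by k/n. If it does not occur, nothing changes. The direction follows from the definition, since substitution cannot make the figure too low. The size depends on an unknown number of substituted patients and an unstated number reached. The proportion remains valid for the narrower question of whether the target PIM stayed stopped or reduced. This is a worthwhile, inexpensive improvement to a descriptive measure and does not call the Aim 2 evaluation as a whole into question.

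**What to change.** Keep the target-PIM proportion as stated, and say explicitly that it refers to the deprescribed drug. In addition:

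1. At the existing 3-month call, ask which PIMs the patient now takes. Take the PIM prescription item from the medical record at baseline and at 3 months.
2. Apply one list covering every class that the protocol names as a PIM: alpha blockers, central alpha agonists, gabapentinoids, muscle relaxants, Z-drugs, anticholinergics, benzodiazepines and opioids.
3. Beside the stated proportion, and on the same denominator, report as supplementary measures (a) the change in number of PIMs and (b) the proportion with the target PIM stopped or reduced and no new or increased PIM. Both are needed, because a dose reduction alone leaves the count unchanged.

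Measure (b) should supplement the stated measure and not replace it, because it also fails a patient who starts a PIM for an unrelated reason.

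The cost is one added question and one record check per reached patient, and a supplementary figure that may look less favourable. One sentence in the protocol describes the 3-month calls in the past tense, so some may already have been made. For those patients the record comparison may still be possible. The change concerns measurement and reporting only.

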- The deprescribing recommendation will provide providers and patients specific information on potential symptoms that may develop and contact information to the deprescribing clinical program if intolerance develops.
- If a patient experiences intolerance (worsened symptoms), they will have instructions based on an evidence-based protocol (e.g., adjust or stop the taper or seek immediate medical attention) and to contact the deprescribing team. Such a protocol will be specific to each target PIM for the pilot study. These protocols will be developed prior to study initiation and approved by a team of physicians and pharmacists. Medications can be restarted or increased at any time should patient not tolerate deprescribing.
- We will monitor for ADWEs after a month of deprescribing onset by reviewing electronic medical records for documentation of clinical event (e.g., unscheduled visit for a symptom or sign related to deprescribing of the target PIM). We will also communicate with each patient at this point. This communication will assess 1) if patient is tolerating the deprescribing plan and 2) if patient has experienced an adverse drug withdrawal events (ADWEs). Prior to that, patients who have concerns during deprescribing can reach deprescribing team. In that communication, the team will ask specific questions to inquire about ADWEs.
- As part of the clinical program, ADWEs will be immediately reviewed by team geriatric nephrologist ([name]) for immediate management recommendations; serious ADWEs will be communicated to the dialysis provider and/or PCP within 2 business days. We will encourage documentation in the patient's medical record.
- The PI (or designee) will report ADWEs that constitute SAEs to the Duke University IRB within 24 hours of learning about the event. Within 5 business days following the initial report, a Notification of a Problem or Event Requiring Prompt Reporting Form to the Duke IRB. The PI will also report SAEs to the NIA Safety Officer according to their reporting policies (if indicated).

- [REDACTED], a geriatrician who is not associated with the program, will serve as Safety Monitor. ADWEs will be reviewed with him quarterly. We will adjust the protocol if needed.

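### The 3-month sustainability measure pools stopping with any dose reduction and rests on a phone answer that is not tied to the baseline prescription or checked against records the study can reach

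*Combined protocol and SAP*

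**What the plan says.** Under Aim 2 Data collection (Design & Procedures), the outcome is introduced as "change in PIM burden (number of PIMs"), that is, a count. The paragraph headed Change in PIM burden then measures it as sustainability at 3 months: "of those who can be reached, proportion of patients who remain off PIM at at a lower dose at 3 months". The doubled word is evidently a slip for an either/or, because the next sentence says that participants who agreed will be "called after 3 months to see if they remain off PIM or at a lower dose of the PIM". No other source is given for this result.

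Four other places bear on it:

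- The additional Aim 2 data list includes "PIM prescription" and says of the listed items: "This data will be obtained from the medical record and through patient communication for the clinical program". Dose is not named as a field of its own. The list also includes "Presence of adverse drug withdrawal event (ADWE), type of ADWE, and if associated with unscheduled clinic visit and/or serious adverse event".
- The table of deprescribing steps says, for both formats, that the deprescribing is documented in the medical record and with the pharmacy.
- The Aim 2 inclusion criteria say that patients "must use a pharmacy that utilizes electronic prescribing (i.e., Surescripts) so that we can examine medication usage". The stated use is to confirm two refills in the six months before entry.
- Data & Safety Monitoring says: "Medications can be restarted or increased at any time should patient not tolerate deprescribing". It also allows a taper to be adjusted or stopped on intolerance.

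**The concern.** Three features combine. First, stopping a drug and taking less of it are different results, and one pooled proportion does not show how much of each was achieved. Second, lower is a comparison, and the outcome does not say with what; a caller could use the dose prescribed at the time of the recommendation, the dose the patient recalls taking, or the last step of the taper. Third, the answer is self-reported to the program that advised the change, and nothing in the plan would reveal a mistaken one.

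The protocol itself gives reasons for caution. Its background section describes cognitive impairment and polypharmacy as at least twice as common in older dialysis patients as in older adults without kidney failure, and says that responsibility for medicines is shared unclearly among several prescribers. Only advanced dementia is excluded. For Aim 1 the protocol planned to compare bottles with the dialysis unit's list and to follow up discrepancies. No such comparison is stated for the Aim 2 outcome.

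At stake is the description of whether the medication change lasted. Aim 2 data are also meant to inform the sample size of a later trial.

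**Working it through.** The plan gives no target, threshold, power or expected value for this measure, so there is no figure to reproduce. The check sets the text side by side and then shows, with assumed values, how the two problems act.

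**1. What the plan holds and what the outcome uses**

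| Element | Available in the plan | Used for the 3-month outcome |
|---|---|---|
| Starting prescription | Listed Aim 2 data item, from the record and the patient | Not named as comparator |
| Deprescribing step | Documented in the record and with the pharmacy | Not mentioned |
| Refill data | Used for eligibility, six months before entry | Not mentioned |
| Restart or increase | Permitted at any time | No rule for classifying it |
| Status at 3 months | Phone call | Sole stated source |

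The 1-month contact and record review under Data & Safety Monitoring look for tolerance and withdrawal events. They precede the 3-month call and do not verify it.

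**2. Count against pooled proportion**

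Assumed: 20 patients reached, each with one target PIM; 8 off it, 6 at a lower dose, 6 neither.

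- Pooled measure: (8 + 6)/20 = 14/20 = 70%.
- Separately: off 8/20 = 40%; lower dose 6/20 = 30%.
- Change in number of PIMs: 8 fewer among 20 patients, or 0.4 per patient. The 6 dose reductions contribute nothing.

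The same six patients are successes under one definition and unchanged under the other.

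**3. Effect of undetected misreporting**

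Let p be the true sustained proportion among reached patients and f the share of those not sustained who are recorded as sustained. With errors in that direction only,

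apparent proportion = p + f(1 − p).

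| p | f = 0.10 | f = 0.20 | f = 0.30 |
|---|---|---|---|
| 0.40 | 0.46 | 0.52 | 0.58 |
| 0.60 | 0.64 | 0.68 | 0.72 |
| 0.80 | 0.82 | 0.84 | 0.86 |

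For example, 0.60 + 0.20 × 0.40 = 0.68. If all 30 planned patients were assessed, the excess at p = 0.60 would be 30 × f × 0.40 = 1.2, 2.4 or 3.6 patients. Both p and f are assumptions. The 3-month denominator is not stated; up to 30 is the recruitment figure for both formats together.

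**4. Scale**

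Exact (Clopper-Pearson) 95% intervals are 0.41 to 0.77 for 18/30 and 0.36 to 0.81 for 12/20. These describe sampling error only and do not allow for misreported status.

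**The case against.** The strongest reply is that this is a small descriptive pilot. No test, threshold or decision rests on the 3-month figure, and sampling error alone is wider than the shifts illustrated. That is fair and limits the importance of the point. It does not remove it: misreporting in one direction does not average out, and the records that would expose it are within reach.

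A reader might also infer several stronger criticisms that the documents do not support.

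- *That no reference dose is recorded.* The PIM prescription is collected, each recommendation carries instructions, and the deprescribing step is documented. A starting dose is probably retrievable; the outcome simply does not refer to it.
- *That a stalled taper or less frequent dosing is wrongly scored as success.* The Risk/Benefit Assessment counts either dose reduction or discontinuation as deprescribing, so both are real reductions on the plan's own terms.
- *That an interim restart counts as sustained.* The wording speaks of remaining off or lower, which implies continuity. A restart is unaddressed rather than accepted, and intolerance behind it should appear among the withdrawal events collected.
- *That reporting bias would distort a comparison of the two formats.* The plan states a split by format for deprescribing attempts, not for this measure.

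A last objection stands in full: records show what was ordered or dispensed, not what was taken. They should not overrule the patient.

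**Conclusion.** The point holds as a measurement weakness. Aim 2's only 3-month measure of medication status combines two different results, is not linked to the baseline prescription the study collects, and depends on an unverified call although restarts and increases are permitted throughout. Misreported status in patients who are reached would go undetected. The outcome also conflicts with its own introduction as a number of PIMs.

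The size of the error is unknown. The illustrated shift from 60% to between 64% and 72% rests wholly on assumed values and on errors that favour success; errors the other way are possible. That a starting dose can be retrieved is an inference from the data list and the documentation step, since dose is not a named field. The change is worth making because it is cheap and the estimate may be carried forward to a trial. It does not threaten the validity of the pilot as a whole.

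**What to change.** The changes concern measurement and reporting only; they do not touch how any drug is managed.

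1. Name the baseline prescribed total dose of the target PIM as the comparator for a lower dose.
2. Report off and lower dose as two separate proportions of reached patients. A pooled figure may follow.
3. For each reached patient, set the phone answer beside the medical and e-prescribing or refill record at 3 months, including any recorded restart or increase. Report how many disagree, and in which direction.
4. Keep the phone answer as a source in its own right and add a sensitivity proportion that counts only successes consistent with the record.
5. Reconcile the introduction of PIM burden as a count with the later measure that includes dose reduction, either by reporting the count as well or by renaming the outcome.

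The cost is a few data fields and a small record look-up. Part of the text describes the calls in the past tense, so some may be complete; the look-up could still be done afterwards. The resulting figure may be less favourable.

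Three limits need a flag in the data: fills outside the e-prescribing network; old prescriptions that stay active after a patient has stopped; and target drugs not named in the refill criterion. That criterion lists gabapentin, muscle relaxants and anticholinergics, whereas the program also targets alpha blockers, central alpha agonists and Z-drugs, so the availability of refill data for those should be confirmed first.
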